During the double-blind portion of the Dose-Determination Phase (ie, Segment 2), an unblinded Medical Monitor independent of the study team will provide additional oversight for the study, including review of serious unexpected AEs considered related to either CORT125281 or enzalutamide and DLTs.

The DLT-evaluation period will extend from the first dose of CORT125281 through the completion of Cycle 3. The DLT-Evaluable Population will include all patients in Segment 2 who received at least 1 dose of CORT125281 and fulfilled at least 1 of the following:

- Completed 3 cycles of treatment with CORT125281 + enzalutamide and received at least 75% of the study regimen
- Experience a DLT

Patients who are non-evaluable for DLTs will include the following:

- Received <75% of the study regimen for reasons other than toxicity
- Patients who withdraw from the study prior to completion of Cycle 3 for reasons other than toxicity (eg, lost to follow-up, withdrawal of consent, or disease progression)

Patients who are non-evaluable for DLTs will be allowed to continue in the study and receive CORT125281 in combination with enzalutamide. Patients who are non-evaluable for DLTs may be replaced to allow a sufficient number of patients to evaluate DLTs (Section 9.4.1).

After all patients complete 3 cycles of treatment or discontinue treatment, the data will be unblinded and the DRC will meet to review the safety and available PK and PD data. The DRC will evaluate the frequency of DLTs, the DLT rate (number of DLTs in DLT-evaluable patients per week [7-day period] during the DLT-evaluation period), and overall tolerability in their assessment of the dose titration regimen as the Phase 2 RD.

If the DLT rate for the regimen is $\geq 33\%$, alternative titration schemes may be considered as the regimen for the RD, such as greater time increments between dose escalations or limiting the upper range of the regimen to those dose levels corresponding to a DLT rate of $< 33\%$. Once the DRC has determined the RD, patients assigned to Arm B who have not experienced dose reductions due to toxicity will then escalate the CORT125281 dose per the recommended upward titration regimen.

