9.5.4 Analysis of DLTs

To meet the study primary objective of determining the MTD/ biologically active doses of CORT125281 in combination with enzalutamide, the number, percent and duration of DLTs according to the NCI-CTCAE, version 4.03, will be summarized by CORT125281 dose and overall.

The DLT rate per patient-weeks, defined as the number of DLTs normalized to the total duration of exposure (in weeks) to CORT125281 during the DLT-evaluation period for all patients in the same treatment arm, will also be presented.

Analyses of DLTs will be performed in the DLT-Evaluable Population.

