Dose Level	Resulting exicorilant Dosage (QD)		Open-Label Bottle (exicorilant)	Blind-Label Bottle (exicorilant or Placebo) ^a
	Arm A	Arm B		
1 (Starting Dose)	240 mg	240 mg	6 capsules	0 capsules
+1 (First Increase)	280 mg	240 mg	6 capsules	1 capsule
+2 (Second Increase)	320 mg	240 mg	6 capsules	2 capsules

QD, once daily.

Note: The exicorilant dosage will be escalated in 2-week intervals unless there are intolerable Grade 2 toxicities, dose-limiting toxicities, or Grade 3 or greater toxicities attributed to exicorilant (Protocol Section 5.7).

^a Note: The blind-label bottle contains blinded capsules (exicorilant [Arm A] or placebo [Arm B]). During the double-blind portion of the Dose-Determination Phase (ie, Segment 2), an unblinded Medical Monitor independent of the study team will provide additional oversight for the study, including review of serious unexpected adverse events (AEs) considered related to either exicorilant or enzalutamide and DLTs.

After all patients complete 3 cycles of treatment or discontinue treatment, the data will be unblinded and the DRC will meet to review the safety and available PK and PD data. The DRC will evaluate the frequency of DLTs, the DLT rate (the number of DLTs per week [7-day period] during the DLT-evaluation period), and overall tolerability in their assessment of the dose titration regimen as the Phase 2 RP2D. If the DLT rate for the regimen is $\geq 33\%$, alternative titration schemes may be considered as the regimen for the RP2D, such as greater time increments between dose escalations or limiting the upper range of the regimen to those dose levels corresponding to a DLT rate of $< 33\%$. Once the DRC has determined the RP2D,

patients assigned to Arm B who have not experienced dose reductions due to toxicity will have their exicorilant dose escalated per the recommended Phase 2 regimen.

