8.8. Dose Limiting Toxicity (DLT) Analyses

Prior to data unblinding, investigators will review AEs that occurred during the DLT-evaluation period and determine AEs that meet the DLT definition.

Dose-Determination Phase Segment 1

DLT analyses will be performed for DLT-evaluable population for patients in Dose-Determination Phase Segment 1, which include all patients who complete at least 1 cycle (4 weeks) of study treatment for segment 1 patients and have received $\geq 75\%$ of doses for both exicorilant and enzalutamide during the DLT evaluation period, or who discontinue treatment due to toxicity.

Three patient cohorts were enrolled in Dose-Determination Phase Segment 1, which are

- (1) Cohort 1: exicorilant 180mg BID/ enzalutamide 160 mg QD
- (2) Cohort 2: exicorilant 140mg BID/ enzalutamide 160 mg QD
- (3) Cohort 3: exicorilant 140mg BID/ enzalutamide 160 mg QD; No enzalutamide lead-in period

Number of patients with at least 1 DLT and number of DLTs will also be summarized by cohort, and overall.

Dose-Determination Phase Segment 2

DLT analyses will be performed for DLT-evaluable population for patients in Dose-Determination Phase Segment 2, which include all patients who complete at least 3 cycles (12 weeks) of study treatment for segment 2 patients and have received $\geq 75\%$ of doses for both exicorilant and enzalutamide during the DLT evaluation period, (or equivalently, received ≥ 63 days of doses during the first 12 weeks for segment 2 patients), or who discontinue treatment due to toxicity.

Three study regimens will be evaluated for Segment 2 Arm A during the DLT-evaluation period, which are

- (1) Regimen 1: 240 mg exicorilant + enzalutamide
- (2) Regimen 2: 240-280 mg exicorilant + enzalutamide
- (3) Regimen 3: 240-280-320 mg exicorilant + enzalutamide

DLT rate will be calculated for each study arm, study regimen and overall. The DLT rate for each study regimen is calculated as the ratio of the number of DLT-evaluable patients who experience at least one DLT during the treatment of any dose level of exicorilant from that study regimen to all DLT-evaluable patients.

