One patient may experience more than one DLTs during the DLT evaluation period. Maximum Duration of DLTs will be calculated in weeks and is defined as the End Date of DLT – Start Date of DLT for the longest DLT time duration for each subject. Number of patients with at least 1 DLT, number of DLTs, and maximum duration of DLTs will be summarized by study regimen and overall.

DLT rate per patient-week will also be summarized by study arm, study regimen and overall, where the numerator is the number of patients with at least 1 DLT, and the denominator is the sum of patient's treatment duration (in weeks) during the DLT-evaluation period which is calculated as the days of the patients on treatment during the first 12 weeks divided by 7.

Number of patients with at least 1 DLT and number of DLTs will also be summarized by study arm, highest exicorilant dose level received, and overall.

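### In Segment 2 the 33% limit is applied to a DLT rate defined per week in the protocol and SAP 2.3, while SAP 8.8 computes a proportion of patients, so the limit has no single scale

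*Protocol*

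**What the plan says.** **Per week.** Protocol 5.4.2 lists, among the things the DRC evaluates after unblinding, "the DLT rate (number of DLTs in DLT-evaluable patients per week [7-day period] during the DLT-evaluation period". The synopsis, 3.1 and 9.9 carry the same per-week meaning. SAP 2.3 has "the DLT rate (the number of DLTs per week [7-day period] during the DLT-evaluation period".

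**The limit.** The next paragraph of 5.4.2 reads "If the DLT rate for the regimen is $\geq 33\%$, alternative titration schemes may be considered as the regimen for the RD". The synopsis and SAP 2.3 contain the same rule. None of the three changes the definition before applying the percentage.

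**Proportion.** SAP 8.8 states "DLT rate will be calculated for each study arm, study regimen and overall" and then "The DLT rate for each study regimen is calculated as the ratio of the number of DLT-evaluable patients who experience at least one DLT", with all DLT-evaluable patients as the denominator. It does not mention 33%.

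**Per patient-week.** Protocol 9.5.4 adds a rate "defined as the number of DLTs normalized to the total duration of exposure (in weeks) to CORT125281". SAP 8.8 adds one too, "where the numerator is the number of patients with at least 1 DLT". SAP 8.8 also notes that a patient can have more than one DLT. SAP Section 13 lists two changes from the protocol (treatment-emergent period and baseline) and no DLT change.

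**Elsewhere.** In Segment 1 (protocol 5.4.1, SAP 2.2) the 33% is explicitly a share of DLT-evaluable patients. The MTD definition (protocol 5.6, SAP 4.1) and the Expansion Phase limit (protocol 9.8, SAP 8.11) use a DLT rate with 33% and give no scale.

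**The concern.** A percentage limit needs a quantity with a matching unit. DLTs per week is a count over time. It can exceed 100%, it does not depend on how many patients were treated, and it counts a patient with several DLTs several times. A proportion of patients does none of these things.

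DLT is the primary endpoint, and the limit bears on whether the titration regimen goes forward. The DRC applies it after the data are unblinded. If the scale is settled only then, the primary safety criterion is being chosen with the data in view.

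**Working it through.** The documents give no derivation of the 33%, so there is no plan figure to reproduce. The check is how many events or patients meet the limit on each scale.

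**Inputs**
- 16 DLT-evaluable patients: 12 in Arm A and 4 in Arm B (protocol 3.2.1).
- DLT-evaluation period of 3 cycles, 12 weeks (protocol 5.5; SAP 8.8).
- Minimum dosing for evaluability without a DLT: 63 days, or 9 weeks (SAP 8.8). This agrees with 0.75 x 84 = 63.
- Limit: 0.33.

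**Scale 1, per week as written.** Taking the 12-week period as the divisor, 0.33 x 12 = 3.96, so 4 DLTs meet the limit (4/12 = 0.333). The number of patients does not enter. One patient with 4 DLTs meets it, although that is 1/12 = 8.3% of Arm A. For all 16 patients the count is still 4.

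**Scale 2, proportion of patients.** Arm A: 0.33 x 12 = 3.96, so 4 patients (33.3%). Overall: 0.33 x 16 = 5.28, so 6 patients (37.5%). Four patients with one DLT each among 16 are 25%, below the limit, yet they meet it on scale 1. Scales 1 and 2 give the same number for Arm A only because there happen to be 12 patients and 12 weeks, and then only if nobody has a second DLT.

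On scale 2 the rule behaves as such a limit normally does. The probability of at least 4 of 12 is 0.205 at a true DLT risk of 20%, 0.597 at 33% and 0.927 at 50%.

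**Scale 3, per patient-week.** Full exposure in Arm A is 12 x 12 = 144 patient-weeks.
- Protocol 9.5.4 numerator (DLTs): 0.33 x 144 = 47.5, so 48 DLTs, or 4 per patient. At 9 weeks each, 0.33 x 108 = 35.6, so 36 DLTs.
- SAP 8.8 numerator (patients): at full exposure the maximum is 12/144 = 0.083, and at 9 weeks each 12/108 = 0.111.
- Early stopping shrinks the denominator. Let k patients have a DLT, with mean treatment t weeks, and let the others have w weeks. The condition is k / (k t + (12 - k) w) >= 0.33. For k = 12, t must be at most 1/0.33 = 3.03 weeks. For k = 11 and w = 12, t must be at most (11/0.33 - 12)/11 = 1.94 weeks. For k = 10 and w = 12, it must be at most (10/0.33 - 24)/10 = 0.63 weeks.
- Under a constant hazard (an assumption), 0.33 per patient-week is a 12-week risk of 1 - exp(-0.33 x 12) = 98.1%. A 33% risk is -ln(0.67)/12 = 0.033 per patient-week, a tenfold gap.
- In a simulation with constant hazard and treatment stopped at the first DLT (both assumptions), the chance of reaching 0.33 was about 0 at true 12-week risks of 33% and 50%, 0.0004 at 70%, 0.053 at 90% and 0.52 at 98%.

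**Numerators on scale 3.** Three patients with 2 DLTs each give 6/144 = 4.2% under protocol 9.5.4 and 3/144 = 2.1% under SAP 8.8.

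**The case against.** **The limit is reachable.** A reader might infer from scale 3 that the limit can never be met. The documents do not support that. The sentence carrying the limit follows a per-week definition, not a per-patient-week one. Read literally, 4 DLTs meet it. Even per patient-week, early stopping can bring the rate to 0.33, and SAP 8.8 counts only days on treatment and admits patients who stop for toxicity. Practically out of reach is right for that scale; impossible is not.

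**The rule is advisory.** A reader might also infer that the 33% comparison alone decides the RD. It does not. The consequence of meeting it is that "alternative titration schemes may be considered as the regimen for the RD", and the DRC also weighs DLT frequency and overall tolerability. That stands. But the same term, again without a scale, defines the MTD, and the RD may not exceed the MTD.

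**SAP 8.8 already has a workable proportion.** It separates the proportion from the patient-week rate and reports both patients with a DLT and number of DLTs, so no information is lost. Segment 1 points to the same scale, and a sensible committee would probably use it. This stands as an argument that the repair is small. It does not resolve the conflict. SAP 8.8 never ties its proportion to the 33%, SAP 2.3 contradicts it, and the protocol names DLT frequency and DLT rate as separate items, so the rate cannot simply be taken to mean the frequency.

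**Conclusion.** The plan is wrong as written on this point. The Segment 2 limit is attached to a count per week, while the analysis section computes a proportion of patients, and the two can give different answers. In Arm A the per-week reading can meet the limit with as few as 1 patient affected, against 4 of 12 on the proportion scale. Over both arms it takes 4 DLTs against 6 of 16 patients. A per-patient-week reading errs the other way: it would not flag even a regimen causing DLTs in most patients, since 0.33 corresponds to about a 98% risk over 12 weeks. Separately, the patient-week numerators differ between protocol and SAP, and the difference is not declared.

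The counts assume the planned 12 and 16 evaluable patients, a 12-week divisor for the per-week rate, and the SAP 8.8 regimen formula carried over to the arm and overall rows. The 98% figure and the simulated probabilities also assume a constant hazard. The textual conflict depends on none of these. Whether 33% is a suitable limit is not judged.

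**What to change.** Reconcile the texts so that one scale, one numerator and one denominator are stated wherever the 33% limit or its rate is used: the synopsis, protocol 3.1, 5.4.2, 5.6, 9.8 and 9.9, and SAP 2.3, 4.1, 8.8 and 8.11. The proportion of DLT-evaluable patients with at least one DLT is already the scale in SAP 8.8 and in the Segment 1 rule, so adopting it throughout would need no new quantity. SAP 8.8 should say explicitly which of its rates is compared with 33%.

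Keep the time-based quantity as a descriptive summary under its own name, such as DLT incidence per patient-week, and state that the limit does not apply to it. Use the same numerator in protocol 9.5.4 and SAP 8.8, or declare the difference in SAP Section 13.

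The cost is SAP wording and a protocol clarification, settled before the Segment 2 unblinding. It needs no extra patients or data and no change to the 33% value.

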5.5 Definition of Dose-Limiting Toxicities

DLTs will be recorded during the DLT-evaluation period (first dose of CORT125281 through completion of Cycle 1 for Segment 1, and first dose of CORT125281 through completion of Cycle 3 for Segment 2). A DLT is defined as any of the following toxicities that the Investigator considers possibly or probably related to study drug that occur during the DLT-evaluation period:

- Hematologic DLT:
 - Grade 4 neutropenia for > 7 days
 - Febrile Grade 3 or 4 neutropenia ($ANC < 1000/mm^3$ and a single temperature of $> 38.3^\circ C$ [$101^\circ F$] or a sustained temperature of $\geq 38^\circ C$ [$100.4^\circ F$] for more than 1 hour)
 - Grade 3 thrombocytopenia with bleeding
 - Grade 4 thrombocytopenia
- Non-Hematologic DLT:
 - Grade 3 or greater toxicity according to NCI-CTCAE v4.03 that represents at least a 2-grade increase from baseline and is not attributable to disease or disease-related processes, with the following exceptions:
 - Grade 3 fever
 - Grade 3 fatigue, nausea, vomiting, constipation, or diarrhea that resolves to Grade 2 or less within 48 hours after standard therapy
 - Grade 3 changes in electrolytes not associated with signs or symptoms and that resolve within 3 days off therapy. An increase in gamma-glutamyl transferase or ALP alone will not be considered a DLT.
 - Transient Grade 3 increase in creatinine or dehydration lasting < 24 hours, corrected with IV fluids if needed
 - $ALT > 3 \times ULN$ with concomitant total bilirubin of $> 2 \times ULN$
- Grade 2 toxicity that represents at least a 2-grade increase from baseline, which requires dose modification or delay of > 1 week
- Failure to receive $> 25\%$ of the doses during the DLT period due to toxicity
- Dose delay due to AE of greater than 2 weeks

Overall tolerability and DLTs occurring after the DLT-evaluation period will be considered by the DRC for the dose escalation decisions.

5.6 Maximum Tolerated Dose

The MTD for CORT125281 in combination with enzalutamide is the highest dose at which the DLT rate is $< 33\%$ within the DLT-evaluation period. The DRC may determine a biologically

active dose of CORT125281 prior to reaching MTD based upon reliable evidence of GR antagonism and assessment of exposure-response for PD, tolerability, and efficacy. The RD of CORT125281 in combination with enzalutamide will take into account overall tolerability, PD markers of target engagement, and PK. The RD will always be \leq MTD.

5.7 Dose Modifications or Delays

If a patient experiences an AE that results in a delay in starting a cycle or requires that study regimen is delayed or interrupted during a cycle, the patient will complete the planned activities per the SoA ([Appendix A](#)) until resuming treatment. All toxicities, with the exception of non-treatment-related, clinically insignificant laboratory abnormalities, should be resolved to Grade 1 or baseline prior to initiation of a new cycle of therapy.

5.7.1 CORT125281 Dose Modification or Delay

If a patient experiences a toxicity of Grade 3 or greater, or an intolerable side effect, withhold enzalutamide and CORT125281 dosing for 1 week or until toxicity improves to Grade 1 or less, or to the patient's baseline. If the toxicity is attributed to CORT125281, resume CORT125281 at a reduced dose.

In Dose-Determination Phase Segment 1, the CORT125281 dose will be reduced to the next lower dose level as indicated in [Table 7](#), or at least by 25% if the dose is below Dose Level -1.

In Dose-Determination Phase Segment 2, the CORT125281 dose will be reduced in 40-mg increments from the current dose level, without unblinding the patient's treatment assignment (exceptions noted in [Section 5.12.2.1](#)), by reducing the number of capsules from the open-label bottle (the active drug) by 1 for each dose level as indicated in [Table 9](#). Additional PK assessments will be collected in all patients that have a dose reduction to enable exposure-response evaluation at the lower CORT125281 dose ([Table 21](#)).

Table 9 Dose Reductions of CORT125281 for Dose-Determination Phase Segment 2

Before Reduction ^a			First Dose Reduction ^b			Second Dose Reduction ^b		
Dose Level	No. of Capsules from Each Bottle		CORT125281 Dose	No. of Capsules from Each Bottle		CORT125281 Dose	No. of Capsules from Each Bottle	
	Open-Label	Blind-Label		Open-Label	Blind-Label		Open-Label	Blind-Label
+2	6 caps	2 caps	Prior dose – 40 mg	5 caps	2 caps	Prior dose – 40 mg	4 caps	2 caps
+1	6 caps	1 cap	Prior dose – 40 mg	5 caps	1 cap	Prior dose – 40 mg	4 caps	1 cap
1c	6 caps	0 cap	Prior dose – 40 mg	5 caps	0 cap	Prior dose – 40 mg	4 caps	0 cap

cap, capsule; No., number.

Note: The open-label bottle contains CORT125281 and blind-label bottle contains blinded capsules (CORT125281 [Arm A] or placebo [Arm B]).

^a. Reduce CORT125281 by 40 mg according to the current dose level.

^b. If a CORT125281 dose reduction is needed, the patient will have additional PK assessments ([Table 21](#)) after 14 days at the lower dose level to enable exposure-response evaluation at lower CORT125281 doses.

Once the dose has been modified for toxicity, re-escalation is not allowed.

If CORT125281 is discontinued, enzalutamide will be continued per the guidance provided in Section 5.7.1.1.

5.7.1.1 Continuation of Enzalutamide After CORT125281 Interruption/Discontinuation

The following guidelines apply for enzalutamide continuation in patients who discontinue CORT125281 or have a CORT125281 dosing interruption:

1. Patients may resume enzalutamide prior to resuming CORT125281 after the Investigator discusses with the Medical Monitor. The intent is for patients to maintain the dose intensity of enzalutamide per standard practice whenever possible.
2. For patients who have not progressed on enzalutamide or second-generation anti-androgen, if CORT125281 is discontinued, enzalutamide will be continued. Following the visit of the subsequent cycle (after discontinuing CORT125281), if all toxicities attributed to CORT125281 have resolved, study visits will occur at least every third cycle until discontinuation of enzalutamide (Section 7.3.1). Upon discontinuation of enzalutamide, the patient will return for the EOT and EOT +30 Days Visits.
3. Patients previously progressing on enzalutamide or second-generation anti-androgen will discontinue enzalutamide, if CORT125281 is discontinued.

Radiographic tumor assessments (CT/MRI, bone scan) should be continued until disease progression per the SoA (Table 16).

5.7.1.2 Monitoring for Excessive Glucocorticoid Receptor Blockade

Based on the mechanism of action of CORT125281, there is the possibility that patients could experience signs or symptoms related to excessive GR antagonism. If signs and/or symptoms of excessive GR antagonism such as malaise, fatigue, lethargy, weakness, anorexia, nausea, vomiting, abdominal pain, altered mental status, or hypoglycemia are present, particularly if co-existent, treatment with CORT125281 should be interrupted and the Medical Monitor should be consulted to assist in evaluating whether treatment should continue. Since CORT125281 does not block the mineralocorticoid receptor, it is unlikely that hypotension would be seen in the absence of anti-hypertensive medication. It is unlikely that hypoglycemia would be observed in the absence of glucose lowering medications.

If excessive GR antagonism is suspected, standard supportive care (including fluid resuscitation as indicated) and medical therapy should be administered without delay. Systemic administration of corticosteroids should be considered (eg, dexamethasone 4 mg daily for 3 days and then tapered by 1 mg per day, or as indicated based on clinical response).

████████████████████ In the event of significant trauma or surgery through 28 days after the final dose of CORT125281, supplemental GCs and appropriate medical care may be needed to prevent excessive GR antagonism that may arise due to increased cortisol requirements in the perioperative period.

